6 STUDY SETTING

This study is being conducted with Major Trauma patients from St George's Hospital.

Participants who consented to take part will be offered to have the interview conducted face to face in line with an upcoming outpatient appointment for their convenience or they will be offered to conduct the interview via the video teleconference (Microsoft Teams).

Face to face interviews will be carried out in private clinical room at St George's hospital. Where interviews are conducted over the phone, the researcher conducting the interview will be in a private space and ensure the patient being interviewed feels they suitable location to conduct the interview. All interviews will be recorded.

7 SAMPLE AND RECRUITMENT

7.1 Eligibility Criteria

Patients at St George's hospital who underwent treatment for Major trauma injuries who had exposure to using the VR Headsets as an adjunct to their rehabilitation will be eligible for the study

7.1.1 Inclusion criteria

Participants aged 18 and over

Who sustained Major Trauma injuries as per the TARN inclusion criteria who used physically active
 Virtual reality headset as an adjunct to their rehabilitation on the major trauma ward

7.1.2 Exclusion criteria

- Unable to speak fluent English
- Those who lack capacity to engage in the formal consent process or where the treating clinicians (e.g.
 doctor or occupational therapist) feels that there is cognitive impairment present that would impact the
 patient from engaging in an in-depth semi-structured interview
- A prisoner or vulnerable adult who will have difficulties organising and attending a face-to-face or over the phone interview safely and conveniently

7.2 Sampling

The study will recruit 10-15 participants using a convenience sampling method.

7.2.1 Size of sample

The study will aim to recruit 10-15 participants. This sample size is similar to other interview studies looking at VR health interventions, with samples of 12 and 14 participants (Deighan *et al.*, 2024; Healy *et al.*, 2023). The rationale for this sample size also considers the researchers time availability to gather data.

7.2.2 Sampling technique

Convenience sampling is also being used. Renjith et al. (2021) state how this process involves collecting data from subjects who are accessible, in geographical proximity and with low-cost implications. Given an opportunity may be missed to approach a patient that is eligible, and participants might be approached who are due to come in for appointment at a time convenient to them and the researcher, this study will also be using a convenience sampling method.

7.3 Recruitment

7.3.1 Participant identification

In the Trauma and Orthopaedic team at St George's we have split clinical and research roles that work across the T&O department as treating therapists and within research. These staff members have training in Good Clinical Practice (GCP) and will appear on the study delegation log. They will be responsible for patient identification and recruitment.

There are two main methods for identifying patients:

- Major trauma Physiotherapists and occupational therapists who are using the Virtual Reality (VR)
 headset with major trauma inpatients will highlight the patients to the research team. The Research
 physiotherapists that work within the Trauma and Orthopaedic team will formally screen the
 patients for eligibility. The chief investigator and delegated research physiotherapists will approach
 the patients on the ward to invite them to participate in the study.
- 2. The Major trauma therapy team is due to start another trust approved quality improvement project in September 2024 on the use of the VR headsets in Major Trauma. The patients who have used the VR headset as part of their inpatient rehabilitation are being asked if they would mind being contacted, after discharge, by the T&O therapy team about future research or quality improvement projects relating to VR in Major Trauma. If they agree to this, it is being documented within their medical notes and being recorded as part of the quality improvement project. Therefore, there will also be a list of potentially eligible patients that could be approached by the research physiotherapists over the phone to invite them to participate. Anyone approached and consented via this method will undergo interview within 12-months or having used the headset, to ensure recent exposure to the device and more accurate reflections on their experience.

The research physiotherapists responsible for approaching patients are experienced in major trauma rehabilitation and can assess patients' mental capacity and ability to provide consent. If the research physiotherapists are having doubts regarding English language fluency and, or cognitive impairment preventing them from participating in an interview, they will utilise the treating clinicians to reach this decision. If a patient is identified as eligible, the research physiotherapists will approach the patients verbally to discuss the study and confirm eligibility with the patient. If the patient is interested in participation, they will be provided with a patient information sheet (PIS) and given then opportunity to ask questions. The Research Physiotherapists will allow the patients 24 hours and more time if necessary to review in the information and further opportunity will be given to ask questions. If the patient is agreeable to the study they will initiate a formal consent process.

7.3.2 Consent

Both in-person and verbal consent methods via the phone will be made available to the patient based on the patient's preference. The research team will ensure that the patient has read the Patient Information Sheet (PIS) (See Appendix 4) which details the nature of the research, the risks involved with participation and emphasises the right to withdraw at any time. The patient will be given time to ask any questions and have key points of PIS verbally re-iterated to them, this will be documented in the clinical notes.

In-person consent

For patients approached face-to-face they will be provided with a paper consent form. Consent will be taken either on the ward or during an outpatient appointment following their discharge. Participants will be asked to read the ICF and initial each box on the consent form (see appendix 5). They will sign and date the bottom of the form alongside the researcher taking consent. The Researcher will indicate on the consent form that consent was taken in person. A copy of the consent form will be uploaded to the participants clinical notes and the participant will be provided a copy. The original version of the ICF will be stored in a file separate to any identifiable information about the patient, this file will be kept in locked storage unit only accessible to the trauma and orthopaedic research team, the storage unit will be kept in a locked room.

Verbal consent

Consent will be completed over phone. The researcher will utilise the same paper version of the ICF and read out each point to the participant over the phone. Each box will be initialled with researchers' initials, they will write the patients name and the date consent was taken and then the researcher will put their own name, signature and date confirming they took consent. The box indicating a verbal consent process was used will be ticked. The patient must be sent a copy of the consent form electronically of via post according to the patient preference. This process will be documented in the clinical notes. An original copy of the consent form will be stored in the same way as face-to-face consent version.

7.3.3 Data collection tools

Sociodemographic data collection tool

A short demographic questionnaire will be taken with patient following consent prior to interview. This will capture information regarding age, mechanism of injuries, what the patient injured, length of hospital stay how many times they used the VR headset, ethnicity, working status, education status. Where possible this will be obtained from the medical notes, missing information will be confirmed with the patient. See **appendix 6** for sociodemographic data collection tool.

Semi-structured interview tool

An interview topic guide has been designed to guide the participants 30-minute interviews to ensure similar content coverage and style of questioning across participants.

This Semi-structured 30-minute interview will be conducted conversationally with one respondent at a time (Adams, 2015). Predominantly open-ended questions will be asked however a blend of open and closed

questions will be used, accompanied by follow-up questions as appropriate, this process aligns with guidance given by Adams (2015) on conducting semi-structured interviews.

The development of the interview topic guide has been informed by clinically relevant existing research and theory. Questions about patients' experience based on topic guides used other interview study exploring patients' views of rehabilitation study after physical trauma (Connolly *et al.*, 2024). Questions assessing the patients' perceived acceptability of the intervention were informed by the TFA and the TFA questionnaire(Sekhon, Cartwright and Francis, 2022) (See Appendix 7).

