APPENDIX 7 Indicative Interview Topic Guide.

Indicative interview topic guide (version 1.0)

Brief opening statement

Thank you for agreeing to participate in this interview today. The interview should last for around 20-30 minutes, and we will mainly focus on your views of the virtual reality headset that used as part of your rehabilitation. You are free to not answer questions if you don't want to, just ask me to move on. We can pause the interview at any point to take a break. Are you happy to continue?

Q.1) Could you begin by telling be briefly about why you were admitted to our trauma unit?

Prompt: What was the incident that led to your injury?

How did this impact you while you were in hospital?

Q.2) You were offered rehabilitation while you were in hospital. What did rehabilitation involve for you? [prompt for all rehab activities, not just VR]

Prompt: Who was involved?

What actions/ exercises?

How much? How often?

Q.3) I understand that / you mentioned that VR headsets were used in your rehabilitation. Can explain to me what they are and how you used them?

Prompt:

- Were you standing or sitting or walking or moving when using the headset?
- What was it like when you put the headset on?
- What could you see? How realistic were the images/ sounds?
- How did it feel to wear the headset?
- What were you asked to do when the headset was on?

Affective attitude

Q.4) Did you like using the VR headsets?

Prompts: What did you like about using the headsets? [get specifics, prompt for more]

Was there anything you did not like about using the headsets? [get specifics (e.g. discomfort, disorientation, prompt for more]

Burden

Q.5) Did you find it easy or difficult to use the headsets? * Try to get participant to distinguish between using the VR and any specific ...

Prompts:

- [If easy] What made them easy to use? / why were they easy to use?
- [If easy] Was there anything about the headsets that made them difficult to use? [e.g. discomfort, disorientation]
- [If difficult] What made them difficult to use?
- [If difficult] Was there anything about the headsets that made them difficult to use?
- During your rehabilitation, how often (and for how long) would you want like wear the headset?

Self-efficacy

Q.6) How confident were you about using the VR headset?

Prompts: Did you feel able to use the headset without help?

Intervention coherence

Q.7) Did you understand why you were asked to use the headset?

Prompts:

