- How was the headset supposed to help your rehabilitation?
- Was there any advantage to using the headset (compared to not using it)?
- Did it make sense to you to wear the headset to help your recovery? [why?]

Perceived effectiveness

Q.8) Do you think using the headsets helped your rehabilitation? [how? why?]

Prompts:

- Did the headsets help you to recover more quickly?
- Did the headsets help you to recover more completely?
- If you had not used the headsets do you think you would have recovered as well as you have?

Opportunity costs

Q.9) Did the time and effort that it takes to use the headset prevent you from doing other activities that are important to you?

Prompts:

- Did using the headsets stop you from resting, reading, talking to family/ friends?
- Did using the headsets stop you from engaging in other important rehabilitation activities?

Ethicality

Q.10) Do you think there are any ethical issues raised by the use of the headsets for patients like you?

Prompts:

- Did somebody explain the reason for using the headsets to you before you were invited to use them?
- Did you feel that you could have refused to use the headsets if you had wanted to? [Did you feel
 pressured into using them?]
- Did you have any concerns about safety risks or side-effects of using the headsets?
- Did the headset make you feel vulnerable?
- Do you think the headsets would be appropriate for all patients? [Would any patients not be able to use them?]
- Are you concerned about the headsets collecting personal data about you?
- Did you feel embarrassed wearing the headset? [are they childish?]

Q.11) Overall, would you that using the headsets was an acceptable part of the rehabilitation process or not? [Prompt for elaboration / explanation]

That's all my questions for you, but before we finish:

Q.12.) Is there anything else that you would like to tell me about your experience of using the headsets?

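### The acceptability questions in the topic guide (Appendix 7, Q4-Q11) are mostly closed, although section 7.3.3 promises mainly open questions; the Q7 advantage prompt and Q8 ask only about benefit, and Q5 contains a duplicated prompt

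*Protocol*

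**What the plan says.** Section 7.3.3 (Semi-structured interview tool) describes a conversational 30-minute interview in which "Predominantly open-ended questions will be asked", although open and closed forms will be mixed and followed up as appropriate. It says the guide is there to secure similar coverage and a similar style of questioning for every participant. Section 3 rests the methodology on open questioning that yields rich description. Section 5 (Data Analysis) then codes transcript text into the seven constructs of the Theoretical Framework of Acceptability (TFA) and builds themes inductively within each one.

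Appendix 7 is labelled indicative, version 1.0. Q1-Q3 set the scene, Q4-Q10 take the seven TFA constructs in turn, Q11 asks about overall acceptability, and Q12 invites anything further. Typical items are:

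- Q4 lead: "Did you like using the VR headsets", with the later prompt "Was there anything you did not like about using the headsets".
- Q5, second prompt of the branch for those who found it difficult: "If difficult] Was there anything about the headsets that made them difficult to use".
- Q7 prompt: "Was there any advantage to using the headset (compared to not using it".
- Q8, first prompt: "Did the headsets help you to recover more quickly".

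**The concern.** Section 7.3.3 describes one style of questioning and most of the acceptability block is written in another. Because the guide is what standardises style, its wording is likely to be what participants hear.

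The analysis needs text under each construct. A bare no to a yes/no question on opportunity costs leaves little to code and less to build a theme from. With 10-15 participants interviewed in a cross-sectional design, thin answers are hard to recover later. Section 2 criticises the pilot questionnaires for giving only a limited view of what patients thought, and section 8.4 records that the patient and public group preferred interviews because they convey individual experience better. A largely closed block risks repeating that limitation.

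The interviewer's position adds some weight. Section 5 (Rigour) acknowledges that the researcher already uses VR clinically and may hold prior views of its benefits. The safeguards listed there, a reflexive approach and review of themes by academics without VR experience in this setting, act on the analysis and not on how questions are put.

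**Working it through.** No sample-size or power figure bears on this point; the check is a count of the items in Appendix 7.

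**Coding rule.** Closed means yes/no or forced choice in grammatical form. Open means what, how, why or who, or an invitation to tell or explain. Each lead question and each prompt line counts as one item.

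| Question | Lead | Prompts | Closed prompts |
|---|---|---|---|
| Q4 Affective attitude | closed | 2 | 1 |
| Q5 Burden | closed | 5 | 2 |
| Q6 Self-efficacy | open | 1 | 1 |
| Q7 Intervention coherence | closed | 3 | 2 |
| Q8 Perceived effectiveness | closed | 3 | 3 |
| Q9 Opportunity costs | closed | 2 | 2 |
| Q10 Ethicality | closed | 7 | 7 |
| Q11 Overall | closed | 0 | 0 |

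**Acceptability block (Q4-Q11).** Leads: 7 of 8 closed. Prompts: 2+5+1+3+3+2+7 = 23, of which 1+2+1+2+3+2+7 = 18 are closed. Together: (7+18)/(8+23) = 25/31 = 81%.

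**Whole guide.** Q1-Q3 have 13 items, 1 closed. Q12 is one item, closed in form. Total: (1+25+1)/(13+31+1) = 27/45 = 60%.

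**More lenient coding.** Four closed items in Q4-Q11 carry their own elaboration probe: the Q4 dislike prompt, the last Q7 prompt, the Q8 lead and Q11. Counting these as open gives (25-4)/31 = 21/31 = 68% for the block. Counting Q12 as open too gives (27-4-1)/45 = 22/45 = 49% for the whole guide. The block stays mostly closed, and the guide as a whole is then about evenly split.

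**Where probes are missing.** Q9 has none on its lead or either prompt. In Q10, four of the seven prompts have no bracketed follow-up, and the three bracketed follow-ups are themselves yes/no.

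**Direction of the 25 closed items in Q4-Q11.** About 10 lean positive, 11 negative and 4 balanced (10+11+4 = 25). That coding puts the third Q8 prompt among the positives. It asks whether recovery would have been as good without the headset, so a yes means no benefit; moving it gives 9, 12 and 4. Neither count shows a positive majority.

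**Q7 and Q8.** The Q7 advantage prompt has no disadvantage counterpart. The Q8 lead and first two prompts ask only about benefit, and no Q8 prompt asks whether the headset hindered recovery.

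**Q5 branches.** The branch for those who found it easy asks what made it easy, then whether anything was difficult. The branch for those who found it difficult asks what made it difficult, then whether anything made it difficult. Ease is never asked about there. The interviewer note on the Q5 lead also stops mid-sentence.

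**The case against.** The best defence is that this is an indicative guide to a conversational interview. Section 7.3.3 openly allows a mix of open and closed questions, Q1-Q3 are open in 12 of 13 items, and a skilled interviewer will not stop at yes or no. This stands in part: it makes thin data a risk and not a certainty. It does not remove the mismatch, because the same section uses the guide to fix style and the open items are concentrated in the scene-setting questions.

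A reader might go further and infer any of the following. The documents do not support them.

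- *The guide is framed positively and steers patients towards calling VR acceptable.* The closed items are roughly even in direction. Q4 asks about dislikes, Q9 asks only about costs, Q10 asks about pressure, safety, vulnerability, data and embarrassment, and Q11 is two-sided. The Q5 slip draws out more difficulty, so it works against approval.
- *Q8 asks what patients cannot know.* The TFA construct is perceived effectiveness. The patient's belief is the intended datum, and an interview can properly collect it.
- *The guide cannot fit the time.* The opening statement says "The interview should last for around 20-30 minutes", and dividing that by every line gives an alarming figure. But prompts are optional. Twelve leads in 1,200 to 1,800 seconds allow 100 to 150 seconds each.
- *Prompts on pain, motivation or anxiety are required.* The approach to experience in section 3 is inductive, and supplying the hoped-for benefits could itself lead participants. The Q8 probe and Q12 leave room to raise them.

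**Conclusion.** The point holds in a limited form, with moderate severity. The acceptability block is 81% closed by grammatical form (25 of 31), or 68% under the lenient coding, against a stated mainly open style. The whole guide is 60% closed, falling to 49% under the lenient coding, so the contradiction is firm for Q4-Q11 and weaker for the guide as a whole. The consequence is possible thin text for some constructs, most clearly opportunity costs and ethicality. One-sidedness is real but confined to the Q7 advantage prompt and Q8. The duplicated Q5 prompt and the unfinished note are plain drafting errors.

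The conclusion rests on two things: the coding rule above, and the assumption that interviewers will largely follow the printed wording, as the aim of a common style implies. How much data would be lost cannot be estimated from the documents.

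**What to change.** Revise Appendix 7 before the first interview:

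1. Reword the Q4, Q5 and Q7-Q11 leads as neutral open questions. For Q8, for example: *What difference, if any, for better or worse, did the headset make to your rehabilitation?*
2. Keep the yes/no items as follow-ups, each with a why or how probe, notably in Q9 and Q10.
3. Add a disadvantage or hindrance counterpart to the Q7 advantage prompt and to the Q8 benefit prompts.
4. Change the second Q5 prompt for those who found the headset difficult so that it asks what was easy, and complete the interviewer note.

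The cost is a redraft of a version 1.0 guide, with no extra participants, visits or staff. Section 8.2 names the interview tool among the documents sent for ethical opinion. The protocol does not show whether that opinion has been given; if it has, the revised guide would go through the amendment route in the same section.

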8 ETHICAL AND REGULATORY CONSIDERATIONS

8.1 Assessment and management of risk

The study is low risk but the main risks identified are as follows:

Risk 1. Topics covered in the interviews could provoke distressing thoughts or emotions

The study will not aim to elicit strong emotional responses; however, patients will be asked to reflect on a period of their recovery from traumatic injury which may understandably cause this.

Risk 1 Mitigation:

To mitigate the impact of potentially distressing topics, participants will be reminded at the start of every interview (and throughout, as required) that they can decline to discuss any topics that they are uncomfortable talking about and take a break at any time. Also, they will be advised that the interview can be stopped and resumed at another time, according to the participants need.

They will also be reminded that the study is optional and that they can withdraw from the study (and retract their interview data) at any time, without question or impact to their future healthcare. As an experienced physiotherapist and researcher, the researcher (BK) is able to recognise more severe stress reactions and in these circumstance participants will be signposted to appropriate psychological service or other post trauma services in the hospital, depending on the issues identified.

Risk 2. Confidentiality and data protection

Participants have a right to anonymity. They will consent to quotes from the interview being used in research reports, but their identity must be protected. The risk of unintentionally identifying participants can sometimes be greater when participants are recruited from a narrowly defined population (e.g. patients undergoing VR-enhanced rehabilitation in a Major Trauma Centre in London).

Risk 2 mitigation:

To mitigate the risk of unwittingly identifying participants, steps will be taken during each stage of the research process (data collection, data transfer, data storage and reporting):

- Copies of the patient consent forms being sent by email will comply with the trusts NHS encrypted email guidelines which allows secure emails to be sent to globally hosted email services.
- Copies of consent forms requested from the patient by post, will be sent in accordance with trusts NHS external posting systems and marked Private & Confidential.
- Interviews will be conducted in a private space.
- If an interview is conducted over video call, the researcher will ensure the patient is in a private space
- Interviews will be recorded onto an encrypted password protected digital device for transfer.
- Identifiable data (i.e. digital audio files of interviews) will be stored in an encrypted file on a password protected PC / laptop at the study site, only accessible by the lead researcher (BK).
- Interview data will be transcribed by [the lead researcher and the transcripts will be fully deidentified prior to analysis (i.e. all identifying information will be deleted, including but not limited
 to: names of patients, healthcare professionals, wards and hospitals; other patient and setting
 details; any information that could alone or in combination reveal the identity of participants). The
 original (potentially identifiable transcripts) will be securely deleted once de-identification is
 completed.
- Participants will be attributed a unique identifier which will be used in all reports, filenames and
 other study documentation. A file linking the unique identifiers to participants' identities will be
 stored in an encrypted file on a password protection PC / laptop, only accessible by the lead
 researcher (BK).
- Demographic and clinical descriptions of the sample will only be presented at the group level, not the individual level.
- All identifiable data (e.g. digital audio files; email correspondence) will be securely deleted on completion of the study (i.e. on completion of the MRes in Clinical Research programme).

The study will be conducted in compliance with GDPR requirements.

COVID-19 Risk Assessment and Management Strategy

All staff employed by SGUL and/or SGH NHS Foundation Trust are required to complete an ongoing COVID-19 risk assessment prior to undertaking any work on site, which includes research activity. This process is continuously monitored by the responsible line manager.

Participants (unaffected or affected) will not be recruited if they are deemed high risk or are in close contact with someone at risk. The Research Team will contact research participants ahead of scheduled study visits on-site to check for COVID-19 symptoms and the symptom check will be repeated when patients attend the hospital site for the study visit.

Participants will receive information regarding the extra precautions that will be taken in light of the COVID-19 pandemic in the PIS. This will detail steps that patients should take if they have concerns about exposure to COVID-19 through participating in the research, or believe that they are symptomatic or have been in close contact with another person believed to be symptomatic. The PIS will also have contact details for the Research Team for patients to get in touch if they have any concerns or queries about this.

All research personnel are expected to comply with the NHS Trust and University policies on COVID-19.

All patients attending the hospital site for research visits and/or routine clinical follow-up will be expected to abide by the NHS Trust and University policies on COVID-19 which include wearing suitable PPE (provided by the NHS Trust on arrival), adhering to the visitor policy on social distancing and following the one-way routing systems whilst on site.

The schedule of study assessments has been designed so that they align with the current routine clinical pathway for this patient population. Additionally, the schedule of study assessment has also been designed to allow for remote consent, recruitment and data collection which is thought to minimise the additional risk of exposure to COVID-19 to both research participants and staff through participation in this research.

Therefore, research participants and site staff are not perceived to be at any additional risk of exposure to COVID-19 through participation in this research study.

